#### **2.4.8.2 *Pulmonary function testing***

The parameters evaluated are DLco (mL/min/mmHg), FVC (L), FEV1(L), TLC (L). Since the local sites use different equations to calculate percent predicted values, the calculation is standardized internally by using the formula provided in [Section 2.1.4.2](#); the percent predicted values calculated at site will remain in the database but will neither be listed nor summarized. The observed values used in analyses are provided by local sites for original study, and will be used for calculation of percent predicted values. The patients transitioning from the pediatric study will continue to use children formula used during the original study even if the age limit prescribed for that formula is crossed during the extension phase.

For all 4 tests, percent (%) predicted values will be summarized for observed values, change from baseline and percent change from baseline using the safety population at scheduled study visit. The analysis of covariance method (including baseline as covariate) and WMW test p-values for the change from baseline and percent change from baseline will be provided in the summary tables for all 4 tests. Box plots of observed values, percent change from baseline for these 4 tests will be provided for the safety population. By-patient plots for all 4 tests over time will be provided.

Analysis of covariance will be used to explore difference among different age cohorts for patients from pediatric study DFI13803, using the following model:

Percent change in percent predicted PFT from baseline = age cohort + baseline percent predicted PFT

For patients from adult study DFI13412, a binary measure of responder (yes vs no) will be derived based on the change from baseline in % predicted DLco at each post-baseline visit. A patient is a responder at the visit, if the patient has change from baseline in % predicted DLco  $\geq 15$ . This binary measure of % predicted DLco will be included in data listing.

#### **2.4.8.3 *Pulmonary imaging - high resolution computed tomography***

A qualitative assessment will be made for the following features: interstitial lung disease (reticular pattern), ground glass appearance, reticulo-nodular density (nodular densities) and pleural thickening of the right and left lungs based on a scale 0-3 as explained in [Section 2.1.4.3](#).

For all 4 features, the mean and standard deviation will be provided for observed values and change from baseline by each side at each level. The mean scores at each scheduled visit are calculated as follows:

Mean score across 4 levels for left (or right) lung = Sum of scores for 4 levels / 4

Mean score across 4 levels and both lungs = (Mean score across 4 levels for left lung + Mean score across 4 levels for right lung) / 2

Summary of the above two types of mean scores and change from baseline for each feature will be provided at scheduled visits. A bar chart for the mean scores across 4 levels and both lungs of each feature will be provided.

#### **2.4.8.4 *Pulmonary imaging - Chest X-ray***

The lung features (interstitial (overall ILD)), reticular, nodular, consolidation and pleura) will be scored subjectively for the degree of diffuse lung disease (infiltrative lung disease) in a scale of 0-3 as explained in [Section 2.1.4.4](#).

For chest x-ray imaging, interstitial provides an overall assessment of interstitial lung disease with reticular and nodular may provide more supportive information on type of interstitial involvement. Consolidation provides a measure of air space disease and is assessed in addition to interstitial involvement. As HRCT provides a more robust characterization of the diffuse lung disease, only interstitial (overall ILD) of the chest X-ray will be analyzed; however data for all features will be provided in data listings.

Summary of mean scores and change from baseline for interstitial will be provided by scheduled visits.

#### **2.4.8.5 *Cycle ergometry***

The parameters of cycle ergometry assessments are noted in [Section 2.1.4.5](#). Percent predicted values (or observed values) will be summarized by scheduled visits along with change from baseline.

#### **2.4.8.6 Physician's global assessment of change**

Frequency shift table for physician's global assessment of disease severity (mild, moderate, severe) from the baseline will be provided at each scheduled post-baseline visit. Frequencies and percentages of patients at each clinical status will be provided at each scheduled post-baseline visit. Seven categories of Clinical Status in Physician's global assessment of change as detailed in [Section 2.1.4.6](#) will be converted to numeric values as follows:

- “Marked improvement of daily activities” = 3.
- “Moderate improvement of daily activities” = 2.
- “Mild improvement of daily activities” = 1.
- “No change” = 0.
- “Mild worsening of daily activities” = -1.
- “Moderate worsening of daily activities” = -2.
- “Marked worsening of daily activities” = -3.

Observed numeric values at each post-baseline visits will be analyzed using analysis of covariance (ANCOVA) model with baseline as covariate. The baseline value will be Physician's global assessment of disease severity at screening with value of 1=mild, 2=moderate, 3=severe.

#### **2.4.8.7 Hematology**

Platelet and hemoglobin are efficacy parameters. At every six month clinic visit these two parameters are evaluated from two blood samples - one for complete blood count, one for hemogram. The average of these two values will be used for efficacy analysis. If and when two values are not available, the single available value will be used.

Observed values, change from baseline and percent change from baseline will be summarized at each scheduled time point. Summary plots of pre-infusion values over time will be provided. By-patient plots over time will also be provided.

For platelet and hemoglobin, analysis of covariance will be used to explore difference among different age cohorts for patients from pediatric study DFI13803, using the following model:

Percent change from baseline in platelets = age cohort + baseline

#### **2.4.8.8 Fasting lipids (including lipoproteins of interest)**

Observed values and change from baseline values will be summarized at each scheduled time point. Summary plots of pre-infusion values over time for each lipid parameters will be provided.

#### **2.4.8.9 Efficacy biomarkers**

Chitotriosidase values will be normalized prior to study analyses based on the patient's chitotriosidase genotype:

Chitotriosidase genotype	Normalization of chitotriosidase activity
Normal	Reported value to be used
Heterozygous	Value multiplied by 2
Homozygous mutation	Value set to "no value"

Observed values, change from baseline and percent change from baseline for efficacy biomarkers will be summarized at each time point. Summary plots of observed values and change from baseline over time for each efficacy biomarker will be provided.

Chitotriosidase genotype and normalized chitotriosidase activity will be listed.

#### **2.4.8.10 Bone disease assessments (Patients from adult study DFI13412)**

##### ***Bone marrow burden***

Observed values and change from baseline values will be summarized at each scheduled time point for total BMB score, total femur score and total spine score separately. Summary plots as well as by-patient plot of observed values over time will be provided.

##### ***DXA parameters***

Observed values and change from baseline values will be summarized at each scheduled time point for BMD, T-score and Z-score by the region of femur and spine separately.

#### **2.4.8.11 Bone biomarkers**

Observed values and change from baseline will be summarized at each scheduled time point. Summary plots of observed values and change from baseline over time for each bone biomarkers will be provided.

#### **2.4.8.12 Bone age by hand X-ray (Patients from pediatric study DFI13803)**

For each patient at each scheduled baseline and post-baseline visits, the difference between the bone age and actual age at that visit will be calculated. Then the change from baseline in the bone age and actual age difference will be analyzed with analysis of covariance (ANCOVA) model with baseline bone age and actual age difference as covariate.

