Olipudase alfa infusion	X	X	X	X	X			
Hand X-ray for bone age				X			X	
Tanner staging					X		X	
Linear patient growth by height Z score		X		X			X	

Study period		Treatment					Post treatment	
Note: The visit schedule is calculated in reference to the first infusion of the patient's previous study. The ± 14 day window applies only to assessments not linked to the time of the infusion. For infusions and assessments closely linked to the time of the infusion (eg, abbreviated physical exams, vital signs), the Q2W visit window of ± 3 days remains.								
Visit/timing	Every 2 weeks (± 3 days)	QV ^a (± 14 days)	QV ^a (± 14 days)	QV ^a (± 14 days)	QV ^a (± 14 days)	Study completion, patient discontinuation or withdrawal ^b	Safety follow-up phone call ^c	
Year 6	W274	W288	W300	W312				
Year 7	W326	W340	W352	W364				
Year 8	W378	W392	W404	W416				
Year 9	W430	W444	W456	W468				
Pediatric health outcome questionnaires (PedsQL, PedsQL Multidimensional Fatigue Scale, PedsQL Pediatric Pain Questionnaire)			X			X		
Pharmacokinetics ^d								
Immune response assessments								
Anti olipudase alfa antibody (IgG)	If introduction of a drug product from Process C () or Process C () occurs, collection will be monthly for the first 6 months after introducing the drug product from the new process							
Neutralizing antibodies	In patients who develop anti-olipudase alfa antibody (IgG)							
IL-6, IL-8, and calcitonin	In case of suspected cytokine release syndrome							
Immune response assessment in case of IAR suggestive of hypersensitivity reaction								
Anti-olipudase alfa antibody (IgG)	At least 3 days after or prior to the next infusion in case of a moderate/severe or recurrent IAR suggestive of a hypersensitivity reaction							
Neutralizing antibodies	In patients who develop anti-olipudase alfa antibody (IgG)							
Anti-olipudase alfa antibody (IgE)	At least 3 days after or prior to the next infusion in case of a moderate/severe or recurrent IAR suggestive of a hypersensitivity reaction							
Serum tryptase and complement activation	Within 1 to 3 hours of a moderate/severe or recurrent IAR suggestive of a hypersensitivity reaction							
Skin testing	If necessary							

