9 ASSESSMENT OF INVESTIGATIONAL MEDICINAL PRODUCT

The term “pediatric patients only” means patients coming from the original pediatric trial, DFI13803. Some of these patients will reach adult age (18 years old) while in this study. These patients will be adults by age, but they will remain part of the “pediatric patient” cohort.

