9.2.7 Hand X-ray (only patients who previously participated in the DFI13803 study)

Patients will have an X-ray performed on their left hand, fingers, and wrist as indicated in [Section 1.3](#) through [Section 1.5](#).

The X-rays will be collected at the site and sent to a medical imaging core laboratory where they will be digitized (if not already done at the site), coded, and read by a third party blinded to patient number and study visit. Bone age (maturation) will be calculated using the Greulich & Pyle Atlas ([17](#)).

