#### **2.1.4.12 Bone age by hand X-ray (Patients from pediatric study DFI13803)**

A hand X-ray is performed for patients who transition from DFI13803 study at Screening and Week 52 in the original study, and will continue every 6 months of exposure to olipudase alfa. Bone age will be provided by the central vendor - BioClinica; they will use calculations based on the Greulich & Pyle Atlas (5).

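### The bone-age ANCOVA has no upper age limit, so a numeric reading of a mature hand would produce a false delay in the older pediatric-study patients

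*SAP*

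**What the plan says.** SAP 2.4.8.12 defines the variable at every scheduled baseline and post-baseline visit: "the difference between the bone age and actual age at that visit will be calculated". It then states that "the change from baseline in the bone age and actual age difference will be analyzed with analysis of covariance", with the baseline difference as covariate. No age or maturity limit is attached.

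Protocol 9.2.7 gives the method: "Bone age (maturation) will be calculated using the Greulich & Pyle Atlas". SAP 2.1.4.12 says that a central vendor supplies the reading and that X-rays "will continue every 6 months of exposure to olipudase alfa". In the protocol flow charts the row "Hand X-ray for bone age" is still present for Years 6 to 9 (Tables 9 and 10).

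Protocol section 9 says of the DFI13803 patients: "Some of these patients will reach adult age (18 years old) while in this study". It adds: "These patients will be adults by age, but they will remain part of the" pediatric cohort. Hand X-ray is a secondary efficacy endpoint (protocol 9.1.2), and SAP 2.4 calls for summaries by age cohort (adolescent, child, infant).

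**The concern.** Bone age measures maturation, which reaches an end point. Actual age does not. After that point the difference reflects only the passage of time, yet the plan keeps analysing it. The baseline covariate cannot remove the fall, because the fall depends on the patient's age and on time since baseline.

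Growth retardation is a named feature of the disease (protocol 4.1), so the direction matters. A falling difference reads as delayed maturation under treatment, and it can cancel real catch-up.

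The SAP deals with ageing elsewhere. It keeps the children's lung-function formula past its age limit (2.4.8.2), restricts change scores when the questionnaire changes (2.4.10.2), and ends the cognitive and adaptive tests at age 6 (2.1.8). Bone age has no comparable rule, and the data-handling conventions in SAP 2.6 do not supply one.

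**Working it through.** The plan gives no figure for this endpoint, so there is nothing to reproduce. The check is direct arithmetic.

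**Inputs from the documents**
- Age at entry to the original pediatric study: under 18 (protocol 4.1).
- Treatment before this study: 64 weeks (notes to the pediatric flow charts). Baseline is taken before the first infusion there (SAP 2.6.1).
- Treatment in this study: at least 3 years for pediatric patients, at most 9 (protocol 6.3).
- Shortest span from baseline: 64 + 3 × 52 = 220 weeks; 220 × 7/365.25 = 4.2 years.
- Longest span: 64 + 9 × 52 = 532 weeks = 10.2 years.

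**Assumptions not in the documents**
- A mature hand receives a numeric bone age, equal to a ceiling C.
- Bone age advances one year per year until C, with a constant delay d (d = 0 is normal maturation).

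**Formula.** With A0 the age at baseline, bone age at time t is min(A0 + t − d, C). The difference is D(t) = min(A0 + t − d, C) − (A0 + t). The analysed quantity is D(t) − D(0). Once the ceiling binds, D(t) = C − A0 − t, which falls by 1.0 year per year whatever C is.

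**Worked case.** A0 = 16, d = 0, t = 4.2. Then D(0) = 0, age at the visit is 20.2, and the change is C − 20.2. That is -2.2 for C = 18 and -1.2 for C = 19. Lower ceilings give more: -3.2 for C = 17 and -4.2 for C = 16.

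False change from baseline, in years:

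| Age at baseline, delay | 4.2 y, C = 18 | 4.2 y, C = 19 | 10.2 y, C = 18 | 10.2 y, C = 19 |
|---|---|---|---|---|
| 16, none | -2.2 | -1.2 | -8.2 | -7.2 |
| 16, 2-year delay | -0.2 | 0 | -6.2 | -5.2 |
| 14, none | -0.2 | 0 | -6.2 | -5.2 |
| 12, none | 0 | 0 | -4.2 | -3.2 |
| 9, none | 0 | 0 | -1.2 | -0.2 |
| 6, none | 0 | 0 | 0 | 0 |

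**Hidden catch-up (C = 18).** Take two patients aged 16 with bone age 14, so D(0) = -2. One catches up fully by 18, a gain of 2 years. The other never catches up. At age 20.2 both read 18, so both have D = -2.2 and change -0.2. The analysis cannot tell them apart.

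**Effect on a cohort mean.** One patient with -2.2 moves the mean of 20 patients by -2.2/20 = -0.11 year, and the mean of 12 by -2.2/12 = -0.18. The documents do not say how many patients are in this position. The SAP gives the pediatric number both as about 20 (1.1) and as 12 (1.3 and 2.4).

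**The case against.** **How a mature hand is recorded is unknown.** A reader might infer that the fall is certain. It is not: neither document says whether the vendor reports a number for a mature hand. If it reports none, the observed-data rule in SAP 2.6.2 drops the visit and the mechanical fall does not occur. This stands as a condition on the point. It does not make the plan safe, because patients who catch up would then leave the analysis first.

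**Size.** A reader might take the raw difference at a given adult age as the bias. The plan analyses change from baseline, so the two agree only when the baseline difference is zero; with a baseline delay the change is smaller. A reader might also want a shift in the whole-cohort mean. The documents do not support one, because ceiling, ages and number of older patients are all missing. Nine years is a maximum, and treatment may end earlier at commercial access.

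**Reach.** This is one of many secondary endpoints in an open-label, single-arm study whose primary objective is safety. Age-cohort summaries, data listings and the Tanner listing would help a careful reader recognise the artefact. They do not correct the ANCOVA.

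**The obvious remedies are flawed.** Stopping at a mature hand depends on the outcome. Suppose two patients aged 16 have bone age 13 and the ceiling is 18. After 4 years one has gained 2 extra years and is mature; the other reads 17. Only the second is kept, with change 0, although the average extra gain is (2 + 0)/2 = 1 year. Stopping at 18 regardless of the atlas may discard valid readings from late maturers. Both criticisms stand and shape the fix.

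**Conclusion.** The point holds, conditionally. As written, SAP 2.4.8.12 keeps analysing bone age minus actual age after maturation can have ended. If mature hands carry a numeric bone age, the change from baseline falls about 1 year per year in those patients.

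Under normal maturation and no baseline difference, a patient aged 16 at the original baseline shows about -2.2 years at 4.2 years with a ceiling of 18, and -1.2 with a ceiling of 19. These are illustrations, not estimates for this trial. Only the slope is free of the assumed ceiling.

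A reader might infer that the whole pediatric cohort would show a false delay. The documents do not support that: they say only that some patients reach 18. The distortion sits mainly in the adolescent cohort, and young children are untouched until late follow-up, if at all. It is a narrow defect in a secondary endpoint, worth correcting because the correction is cheap.

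**What to change.** Amend SAP 2.4.8.12 as follows.

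- Limit the bone-age ANCOVA and by-visit summaries to visits at which the patient's actual age is below the age of the atlas's mature standard for that sex. State both ages in the SAP. This cut-off does not depend on the outcome.
- Exclude patients already past that age at the original-study baseline.
- State how the vendor records a mature hand, and flag such readings. A child whose bone age runs ahead of actual age can reach the ceiling before the cut-off, so some flagged readings may remain in the analysis.
- Report the number of patients contributing at each visit.
- List later X-rays, including any hands that are still immature.
- Present the all-visit analysis only as a sensitivity analysis.

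The cost is a short SAP paragraph and one query to the imaging vendor, with no new X-rays. The price in information is fewer late observations. Valid readings from late maturers past the cut-off are listed rather than modelled, and those patients are of particular interest in this disease, so the listing should be easy to find.

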#### **2.4.8.13 Tanner staging (Patients from pediatric study DFI13803)**

This data will be provided in a data listing.

#### **2.4.8.14 Height z-score (Patients from pediatric study DFI13803)**

The height z-score categories will be summarized for all scheduled visits. Change from baseline in height z-score will be analyzed with analysis of covariance (ANCOVA) model with baseline height z-score as covariate.

#### **2.4.8.15 Subgroup analyses for efficacy (Patients from pediatric study DFI13803)**

For Patients from pediatric study DFI13803, below subgroup analyses will be performed.

To assess persistence of efficacy in patients with different baseline disease severity, the following subgroup analysis will be conducted:

- Spleen volume (MN) by baseline spleen volume severity (severe vs not severe). Severe patients is defined as baseline spleen volume  $>15$  multiple of normal (MN).
- % predicted DLco by baseline % predicted DLco severity (severe vs not severe). Severe patients is defined by baseline % predicted DLco  $<40\%$ .

To assess the impact of immunogenicity on efficacy, descriptive summaries for spleen volume and platelet count will be conducted for the following two groups of patients treated with olipudase alfa:

- Patients with treatment emergent anti-drug antibody (ADA) positive defined as either treatment induced or treatment boosted ADA positive at any time during olipudase alfa treatment.
- Patients with ADA negative defined as neither treatment induced or treatment boosted ADA positive at all time during olipudase alfa treatment.

For all the above subgroup analyses, within each subgroup, the change or percent change from baseline at each longitudinal time point will be summarized and analyzed with the analysis of covariance (ANCOVA) approach with baseline as covariate.

The efficacy measures (spleen volume and platelet count) will also be compared between manufacturing Process B, Process C (█) and Process C (█) as described below.

- To compare Process B and Process C (█), descriptive summaries for above efficacy measures will be created for the patients who started on Process C (█) only (patients never on Process B) versus patients who started on Process B and then switched to Process C (█) (Patients who were ever on Process B). In this analysis, the data when patients were exposed to Process C (█) will be excluded.
- Descriptive summaries for above efficacy measures will be created for the patients who did not switch to Process C (█) yet (patients never on Process C (█)) versus patients who switched to Process C (█) (Patients ever on Process C (█)).
- For patients who switched to Process C(█) and patients who switched to Process C (█) separately, the individual patient plot of observed values at each time point for above efficacy measures will be created with time point for start of each process (B, C (█) and C (█)) added on the plot.

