In a completed Phase 1b, open-label, multicenter ascending-dose study in 5 adult patients with ASMD, the safety and tolerability of olipudase alfa were evaluated during a 26-week treatment period (6). Patients received an initial IV dose of 0.1 mg/kg of olipudase alfa, then the dose was escalated in a stepwise manner to a final target IV dose of 3.0 mg/kg. All patients remained at 3.0 mg/kg for the remainder of the treatment period. Upon completion of the study, all patients enrolled into an open-label, long-term treatment study. Results from this trial demonstrated that the progressive, within-patient olipudase alfa dose escalation regimen was well tolerated in adult ASMD patients. No serious or severe AEs or deaths were reported in the study. Related AEs consisted predominantly of infusion-associated reactions (IARs), most of which were mild in severity with all patients recovering without sequelae. At the end of the 6-month treatment period, a positive response to treatment with olipudase alfa was observed in several individual efficacy parameters. This included mean decreases in spleen and liver volumes by 25.3% and 17.1%, respectively; decreased interstitial lung disease (ILD) scores; increased percent predicted diffusing capacity of the lung for carbon monoxide (DL_{CO}); reduction in serum chitotriosidase, chemokine (CC-motif) ligand 18 (CCL-18), and angiotensin-converting enzyme (ACE); a positive trend

towards a less proatherogenic lipid profile; and, trends for improvement in quality of life assessments for fatigue and pain.

Other clinical studies of olipudase alfa are planned or ongoing. These include:

- A Phase 1/2, multicenter, open-label, ascending-dose study to evaluate the safety, tolerability, PK, PD, and exploratory efficacy of olipudase alfa in pediatric patients aged <18 years with ASMD.
- A Phase 2/3, multicenter, randomized, double-blinded, placebo-controlled repeat-dose study to evaluate the efficacy, safety, PD, and PK of olipudase alfa in patients with ASMD.

A complete summary of nonclinical and clinical experience with olipudase alfa can be found in the investigator's brochure.

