11.1.1 Final analysis

The final analysis will be performed at the completion of the treatment period. This analysis will include safety, efficacy, PK, and PD data. Analyses of change will be based upon changes from baseline prior to olipudase alfa therapy (ie, baseline in the previous study [DFI13412 or DFI13803]) through study completion. The final statistical analyses will be performed when the entire database is locked and signed off, in accordance with the standard operating procedures of the sponsor or designee.

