11.6.2.1 Multiplicity considerations

Not applicable.

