## **2.4 STATISTICAL METHODS**

Data collected in this study will be presented using summary tables, figures, and data listings. Descriptive statistics for categorical variables will be provided using frequencies (n) and percentages (%). Descriptive statistics for continuous variables will be provided using number of observations (n), mean, standard deviation (SD), median, minimum, and maximum. All data used in tabular summaries or figures will be supported by listings of underlying data – raw and/or derived, and all figures will be supported by relevant summary information.

All summaries will be provided for the LTS population, along with separate subgroups in the population according to which original study the patient belonged to: DFI13412 (adult study, Phase 1B, 26 weeks, 5 patients), DFI13803 (pediatric study, Phase 1/2, 64 weeks, 12 patients). In addition, similar summaries will be produced by age cohort of adolescent, child, infant for the patients who transition from pediatric study DFI13803.

The scheduled visits in statistical displays will be labelled in months of total follow up time from the first infusion in the original study. For example, a 6-month visit in this study for a patient transitioning from the 26-week DFI13412 study will be identified as Month 12 exposure in the displays. The schedule of measurements for this study will be followed for display presentation with baseline derived from the original study. For patients in this study, the results from the original study visits will be included, unless specified otherwise, for the purpose of understanding the continuity of treatment effect during this extension phase; for details and descriptions of all results from the original study, please refer to the original study CSR. For parameters that are not collected in the extension phase will not be part of this SAP.

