#### **2.4.8 Analyses of efficacy endpoints**

All efficacy analyses to assess changes in organomegaly (spleen and liver), infiltrative lung disease, pulmonary function, cycle ergometry endpoints, physician's global assessment, hemoglobin/platelet, efficacy biomarkers, lipid profile, bone biomarkers, health outcome questionnaires, will be performed using the safety population. Additional endpoints for pediatric patients include: linear growth (height z-score), bone age, tanner staging and cognitive and adaptive functioning (up to the age of 6 years only).

Baseline for efficacy parameters will be defined as the last non-missing value before the first infusion in the original study, except for hemoglobin and platelet; for complete definition of baseline values, please refer to [Section 2.6.1](#).

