#### **2.4.8.1 *Spleen and liver volumes***

For timing of MRI measuring spleen and liver volume, and the formula for calculating the volumes in multiples of normal (MN), refer to [Section 2.1.4.1](#).

Change from baseline and percent change from baseline for both  $\text{cm}^3$  and MN units, in addition to observed values, will be calculated and summarized for all scheduled visits. The analysis of covariance method (including baseline as covariate) and Wilcoxon-Mann-Whitney (WMW) test p-values (and 95% confidence interval) for the change from baseline and percent change from baseline will be provided in the summary tables for spleen/liver volumes in MN unit. Box plots of observed values for spleen and liver volumes in MN unit will be provided.

The correlation between spleen and liver volumes with other efficacy/safety/pharmacodynamic parameters may be explored graphically.

Analysis of covariance will be used to explore difference among different age cohorts for patients from pediatric study DFI13803, using the following model:

Percent change from baseline = age cohort + baseline

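### The analysis labelled as persistence of efficacy measures change only from the pre-treatment baseline, so it cannot separate maintained benefit from benefit partly lost during the extension

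*SAP*

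**What the plan says.** SAP 2.4.8.15 covers patients from DFI13803. It splits them by baseline severity (spleen volume above 15 multiples of normal; % predicted DLco below 40%) and gives the purpose as "To assess persistence of efficacy in patients with different baseline disease severity, the following subgroup analysis will be conducted". For both severity splits the method reads: "the change or percent change from baseline at each longitudinal time point will be summarized and analyzed with the analysis of covariance (ANCOVA) approach". The covariate is the pre-treatment value. The same ANCOVA applies to the antibody-status subgroups in that section.

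The reference point is fixed in SAP 2.4.8: "Baseline for efficacy parameters will be defined as the last non-missing value before the first infusion in the original study" (hemoglobin and platelets use the average of the pre-infusion values). Protocol 11.1.1 agrees: "Analyses of change will be based upon changes from baseline prior to olipudase alfa therapy". Spleen and liver volume (SAP 2.4.8.1), pulmonary function (2.4.8.2), bone age (2.4.8.12) and height z-score (2.4.8.14) are tested against that baseline. For organ volumes, p-values "and 95% confidence interval) for the change from baseline and percent change from baseline will be provided in the summary tables".

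SAP 2.4 brings original-study visits into the displays "for the purpose of understanding the continuity of treatment effect during this extension phase". The documents define no loss of response, no persistence margin and no summary of change from extension entry.

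**The concern.** Patients enter the extension already treated, for 26 weeks (adults) or 64 weeks (children) according to SAP 2.4. Protocol 4.1 reports "mean decreases in spleen and liver volumes by 25.3% and 17.1%, respectively" in the 5 adults by the end of their first study. A test of change since before the first dose credits the extension with benefit gained earlier. Its null hypothesis is that patients are no better than before treatment, whereas persistence asks whether the position at entry was kept, improved or eroded.

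At stake is how a significant result at a late visit is read. It supports the statement that patients are still better than before treatment. It does not support the statement that the effect was maintained through the extension, and the plan provides no other estimate with an interval that would.

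**Working it through.** The plan states no power, margin or effect-based sample size, so there is no figure to reproduce. The question is how often the planned test would be significant if part of the gain were lost.

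**Inputs from the documents**
- Gain at entry: 25.3% for spleen (Protocol 4.1; adults, 26 weeks). No pediatric gain is given, so applying this to children is an assumption.
- Pediatric n: about 20 (SAP 1.1) or 12 (SAP 1.3 and 2.4). Severity subgroup sizes are not given; n=6 stands for half of 12.
- Test level: not stated. The 95% intervals in SAP 2.4.8.1 suggest two-sided 5%. Protocol 11.6.2.1 on multiplicity says "Not applicable".

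**Assumed**
- SD of percent change: 8 to 15 points.
- The tested quantity is the mean change at average baseline, compared with zero.

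**Formula.** With retained mean m, the one-sample t statistic has non-centrality m√n/SD and n−1 degrees of freedom. Half lost gives m = 0.5 × 25.3 = 12.65; three quarters lost gives m = 0.25 × 25.3 = 6.3.

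Examples:
- n=12, SD 15, half lost: 12.65 × 3.464/15 = 2.92 against a critical value of 2.201, giving 76%.
- n=20, SD 8, three quarters lost: 6.325 × 4.472/8 = 3.54 against 2.093, giving 92%.

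Probability that the baseline test is significant (SD 15 to SD 8):

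| n | Nothing lost | Half lost | Three quarters lost |
|---|---|---|---|
| 6 | over 90% | 39–87% | 14–35% |
| 12 | about 100% | 76–100% | 27–70% |
| 20 | about 100% | 95–100% | 43–92% |

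With all the gain lost, the rate is the nominal 5%.

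**Checks**
- Taking n−2 degrees of freedom for the baseline covariate changes half lost to about 35–82% at n=6 and 75–100% at n=12; n=20 is unchanged.
- On n−2 degrees of freedom, an observed mean of 12.65 has p<0.05 whenever the SD is below 12.65√n/t: 11.2 (n=6), 19.7 (n=12) or 26.9 (n=20).
- For liver, half of 17.1% lost at SD 10 gives 76% (n=12) and 95% (n=20).

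**Change from extension entry instead.** If the correlation between the entry and later values is 0.6 (assumed), the SD of the difference is SD × √(2 × 0.4) = 0.894 × SD, or 8.94 at SD 10. The 95% half-width, t × 8.94/√n, is 9.4 points at n=6, 5.7 at n=12 and 4.2 at n=20. A loss of 12.65 points would be detected with probability 79%, 99% and about 100%. At SD 20 these fall to 29%, 61% and 85%.

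**The case against.** The strongest reply is that the trajectory is already reported. Original-study visits appear alongside extension visits, and observed values and changes are summarized by visit. Spleen, liver and pulmonary function have box plots. By-patient plots are planned for pulmonary function, platelets and hemoglobin, and individual spleen and platelet plots for patients who switched manufacturing process. A mean change moving from −25% to −12% would be visible. Efficacy is a secondary, descriptive objective, the baseline is explicit and consistent across both documents, and nowhere do they say that a significant change from baseline will be taken as proof of persistence.

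Much of this stands. A reader might infer that waning would go unseen; the displays do not support that. What they lack is a within-patient estimate with an interval. SAP 2.6.2 bases summaries of continuous variables on observed data only, so visit means may come from different patients, and no by-patient spleen plot is specified by severity.

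A reader might also infer that the earlier benefit makes the test significant whatever is later lost. The figures do not support that either: at n=6 with half lost the rate may be only 39%, and with everything lost it is 5%. Nor do all the efficacy models share this null. The age-cohort ANCOVAs in SAP 2.4.8.1, 2.4.8.2 and 2.4.8.7 compare cohorts.

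**Conclusion.** The point holds as a mismatch between the stated question and the analysis. The severity-subgroup ANCOVA shows whether patients remain better than before treatment; it does not assess persistence through the extension. Where the test has little power the mismatch remains: non-significance would not show loss, and significance would not show maintenance.

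The size is illustrative. It rests on an adult 26-week gain applied to children after 64 weeks, an assumed SD and assumed subgroup sizes. A larger pediatric gain would raise the percentages; a larger SD or smaller subgroups would lower them. DLco cannot be quantified because the documents give neither a gain nor an SD, and its n may be smaller because SAP 2.1.4.2 limits pulmonary function tests to patients aged at least 5 at original-study screening. It would also go too far to say that the planned null was already false at entry for every endpoint: the documents give figures only for adult spleen and liver volume.

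The change is worth making because it is cheap and answers a question the SAP itself poses. It concerns secondary efficacy reporting, not patient safety.

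**What to change.** In SAP 2.4.8 and 2.4.8.15, add the within-patient change from the last original-study assessment before the first LTS13632 infusion to each extension visit. Do this for spleen and liver volume, % predicted DLco, platelets and height z-score. Report the mean and 95% CI overall and, for spleen volume and % predicted DLco, by severity subgroup. Base persistence statements on this estimate, and note that intervals in small subgroups will be wide. Keep change from the pre-treatment baseline as the display of total effect.

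The cost is one derived variable, a few more tables and some SAP wording; the original-study data are already in the displays. The new figures may look less favourable than change from pre-treatment baseline.
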